6.3. Modification of Study Intervention/Investigational Product for a Subject

Children who experience emesis within one hour of dosing will receive a repeat dose. This will be done only once per subject.

6.4. Accountability Procedures for the Study Intervention/Investigational Product(s)

Praziquantel and Placebo will be stored and shipped from the United States. Once received, Praziquantel and placebo tablets will be stored in locked cabinets and dispensed by the Project leader. Unused product will be locked and disposed of at the study sites following local guidelines.

The Investigator will be responsible for ensuring that a current record of product disposition is maintained and product is dispensed only at an official study site by authorized personnel as required by applicable regulations and guidelines. Records of product disposition, as required by federal law, consist of the date received, date administered, quantity administered, and the subject number to whom the drug was administered.

The Investigational Pharmacist will be responsible for maintaining accurate records of the shipment and dispensing of the investigational product. The pharmacy records will be available for inspection by monitoring contractors, and will be subject to inspection by relevant regulatory agencies at any time. An assigned Study Monitor will review the pharmacy records.

Unused reconstituted investigational product vials will be stored at room temperature at each site until clinical trial accountability is completed. At study termination, all unused investigational product will be disposed in accordance with the MOP following complete drug accountability and monitoring.

6.5. Assessment of Subject Compliance with Study Intervention/Investigational Product/Investigational Device

Subjects will be directly observed at the time of dosing by a member of the clinical research team who is licensed to administer the study product. Administration will be documented on the Treatment Case Report form and entered into the eCRF.

6.6. Concomitant Medications/Treatments

Study participants should not be on any concomitant immune-modulatory treatment, rifampicin, chloroquine, antiepileptic drugs and grape juice all of which are known to alter PZQ metabolism and/or efficacy.

7. SCHEDULE

7.1. Recruitment

Philippines site: Meetings will be arranged with community leaders including village mayors, village health workers and directors of relevant municipal health centers. Field staff will arrange village level information sessions about the study. Flyers will be made available and field workers will additionally contact families with young children in target villages to provide information about the study. Field workers will identify families who are willing to learn about phase one screening activities for the study. Information sheets will be delivered in the households and the screening informed consent will ensue delivered by GCP certified field staff.

Uganda site: Fishing communities along Lake Albert will be approached through organizing community wide meetings. Prior to these, the village chiefs will be contacted to inform them about the project and obtain permission. The meetings will be announced publicly with flyers distributed by community mobilisers who will be in charge of contacting the interested parents after the information sessions have taken place. Information sheets will be delivered in the households and the screening informed consent will ensue delivered by GCP certified community workers.

7.2. Field Based Screening

Both study sites: Screening will take place in two phases. The first phase will occur at the village level with field staff after informed consent for only the initial screening activities (urine sample for CCA testing). Children with a positive antigen test will be considered positive for schistosomiasis and eligible for potential enrolment. Parents will be given two cups (three in the Philippines) to provide stool samples collected on different days to quantify intensity of infection at baseline. Work will be performed by Ministry of Health personnel (Vector Control Division).

7.3. Laboratory Based Screening, Enrollment/Baseline

Philippines site: If children are deemed eligible based on both screening phases, they will be “admitted” to the Palo Field Laboratory for 12 hours. There will be one medical technologist assigned to four children.

Uganda site: If children are deemed eligible based on both screening phases, they will be “admitted” to the Kabatereine Schistosomiasis Research Center in Buliisa District for 12 hours. There will be one nurse assigned to four children. Technical work in this phase will be performed by Ministry of Health personnel (Vector Control Division).

Phase two screening will take place at the field laboratories to ensure other inclusion/exclusion criteria are met prior to enrollment. Specifically, information will be provided which will detail the second phase of screening as well as the full procedures, and informed consent obtained. Phase two screening includes capture of weight and height to determine nutritional status (weight for height z-score), laboratory studies

to rule out severe anemia, physical examination and history to rule out a chronic medical condition that might make deem a child ineligible.

At both sites, the following activities will take place in **ALL** participants:

- History and physical exam
- Weight and height
- A catheter will be placed for blood draws
- Blood collection (5 mL) for complete blood count (CBC) and renal/liver toxicity measures. Serum will also be used for morbidity studies (EED biomarkers, iron biomarkers, and pro-inflammatory cytokines). Before discharge, another blood sample will be removed between 6 – hours after administration of the first dose of the study drug. This enables monitoring for possible toxicity.
- HIV testing and malaria testing
- Lactulose/Mannitol beverage. Children will take a small volume of a lactulose/mannitol at a dose of 2 ml/kg up to a maximum of 20 ml beverage as a measure of gut permeability and gut absorptive capacity and we will collect urine for 2 hours afterwards. They will fast 30 minutes before the lactulose:mannitol administration.
- Ultrasound scan for detection of schistosomiasis-related morbidity.
- **Stool** collection for parasitology by Kato-Katz if two stools not provided prior to enrollment, fecal calprotectin and fecal occult blood (performed on site).
- **PZQ** administration at the study assigned dose after a meal consisting of local foods.
- Final blood collection (3 ml) for CBC, renal, and liver toxicity 12 hours post dosing (all participants)

To participants further randomly selected for pharmacokinetics and immunology sub-studies:

- At each site participants will be randomly allocated into two groups with different blood sampling frequency but similar overall volume (an extra 5 ml)
 - Pharmacokinetic sub-study:
 - In a sub-set of children (N= 150 in both sites) the indwelling cannula will be used to obtain four blood samples of approximately 1 ml for PK/PD studies at respective intervals. Participants who will be sampled for PK/PD studies **will not** participate in the immunology sub-study
 - Immunology sub-study:

- In a sub-set of children in Uganda, 7 ml of whole blood will be collected for immunology assays (such as flow cytometry, Luminex, ELISpot and ELISA).
- Participants who will be sampled for the immunology sub-study **will not** participate in the PK/PD study
- A subset of children without schistosomiasis will be recruited and will provide urine before and after ingesting lactulose-mannitol solution. Stool and 4ml of blood will also be taken for study of gut microbiota/EED biomarkers and morbidity markers.

7.4. Follow up at 4 weeks

Stool will be collected 4 weeks (+/- 1 week) after the baseline visit from parents at their home. Three stools will be collected to quantify egg counts by Kato Katz. Field workers will be responsible for picking up cups at this timepoint for microscopy. Technical work in this phase will be performed by Ministry of Health personnel (Vector Control Division). They will also perform the urine CCA test. **Urine** collection for:

- 2 ml tube collection for CCA/CAA testing
- **Stool** collection for:
 - Parasitology (Kato Katz assessment for schistosomiasis and geohelminths (hookworm, Ascaris, Trichuris).
- Blood- only to those children in the immunology sub-study. 7 ml of whole blood will be collected for immunology assays (such as flow cytometry, Luminex, ELISpot and ELISA).

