1. *Screening* We propose to employ a two stage screening process. The first phase is a village - based survey to identify children who are infected using rapid point of care testing (urine Circulating Cathodic Antigen (CCA)). CCA provides a highly sensitive and efficient means to screen children, with high sensitivity demonstrated in young children.^{18,19 20,21} Two stool samples (taken on consecutive days) will also be collected from every child who is CCA positive prior to the start of the study, at four weeks +/-1 week after treatment, and at 12 months post-treatment to provide a measure of infection intensity. Fecal smears will be prepared from each sample in duplicate applying the thick Kato-Katz technique for the detection of *S. mansoni*, *S. japonicum* and soil-transmitted helminths. Mean egg counts per gram of stool (epg) will subsequently be calculated and three intensity categories will be considered for *S. mansoni* and *S. japonicum* infection: light (1-99 epg), medium (100 – 399 epg) and heavy (>400 epg) as per World Health Organization Guidelines.²²

The second phase of screening will occur at the field laboratories in Palo, Leyte, The Philippines and in Lake Albert, Uganda. Prior to study enrollment, each child will undergo a physical exam and medical history to determine eligibility. Children who are not eligible based on severe malnutrition (WHZ < -3.0), severe anemia (hemoglobin < 7.0 g/dL) or chronic medical condition as defined by a disease lasting longer than three months and impacting a child's daily function or normal activities will be excluded at this stage.²³

1. *Study visit 1/Baseline.* After determination of eligibility, subjects will be enrolled following all screening assessments. Both field stations have a patient intake area with private areas for consenting and physical examinations. At this visit, a small blood drawing catheter will be placed to minimize the number of times children need to have a needle stick. Blood will be drawn for baseline morbidity studies (5 ml). In depth measures of nutritional status will be made, and children will be randomized to receive either 40 mg/kg or 80 mg/kg of Praziquantel either annually or six-monthly (4 arms).

In addition, children will be randomly split into two groups, half will have an extra 7 ml of blood drawn at the time of the morbidity studies (N=150) for immunologic studies and half will take part in pharmacokinetic studies (N=150, further details below).

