To test gut permeability and absorptive capacity, lactulose-mannitol solution (containing 250 mg/mL lactulose and 50 mg/mL mannitol in purified water) will be administered to study participants orally at a

dose of 2ml/kg up to a maximum of 20 ml. Prior to administration of the solution, the child will be fasted for 30 minutes. Breast feeding will continue. A urine bag will be strapped to ensure all the urine is collected. The first urine sample voided will be considered as baseline. A new bag will then be put in place to continue urine collection for 2 hours. Once collected, an aliquot of 2 ml of urine will be stored between 2°C and 8°C having added 2 drops of chlorhexidine. Two hours after ingestion of LM solution, the test will be stopped. If the child has not passed any urine, the test time will be extended until the next urine is voided.

Following the LM test, two doses of PZQ will be administered three hours apart. After receiving praziquantel, all children will stay at the study premises for 3-6 hours with a guardian monitoring side effects. After administration of the second dose of the study product, children will undergo ultrasound scan to determine presence or absence of any pathology related to schistosomiasis. The Niamey Protocol will be used to grade severity of disease.

The subset of children (approximately N=150) who will be randomly selected for PK sampling (four blood draws in total) children will stay at the premises for at least 6 – 8 hours after administration of the initial dose of praziquantel. At the time of discharge, children who will be found to be infected with soil-transmitted helminths will be treated with albendazole 200 mg (12 – 24 month old children) or albendazole 400 mg (children over age two). Blood Chemistry to ascertain renal and liver function will be repeated 6 – 8 hours after administration of the first dose of praziquantel, before discharge.

2. *Study Visit 2.* Stool will be collected 4 weeks (+/- 1 week) after treatment. Two stools will be collected on consecutive days to quantify egg counts by Kato Katz. Field workers will be responsible for picking up cups at this timepoint. No visit to the field laboratories will be required. Urine will be collected for CCA/CAA. Blood (7 ml) will be collected for the same subset of N=150 subjects for studies of immunological responses as at baseline.

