5. STUDY ENROLLMENT AND WITHDRAWAL

5.1. Subject Inclusion Criteria

- *S. mansoni* (Uganda) or *S. japonicum* (Philippines) infection of any intensity as determined by Kato-Katz
- Otherwise healthy as determined by history and physical examination conducted by the study physician at the second stage screening
- Age 12-47 months inclusive
- Parental consent to participate.

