14.3. Informed Consent Process

Informed consent is a process that is initiated prior to the parent agreeing to allow his/her child to participate in a trial and continuing throughout the child's trial participation. Before any study procedures are performed, informed consent of the parent will be obtained and documented. There will be separate consent processes and forms for participation in screening activities (limited to stool and urine collection) and main study activities since only those who have schistosomiasis based on stool examination are eligible to participate in the main study. Subjects will receive a concise and focused presentation of key information about the clinical trial, verbally and with a written consent form. The explanation will be organized, and presented in lay terminology and language that facilitates understanding why one might or might not want to participate.

An investigator or designee will describe the protocol to potential subjects face-to-face. This will occur in a private space in communities for the screening consent and in a private space at the respective research field sites for the main study. The key information about the purpose of the study, the procedures and experimental aspects of the study, risks and discomforts, any expected benefits to the subject, and alternative treatment will be presented first to the subject.

Subjects will also receive an explanation that the trial involves research, and a detailed summary of the proposed study procedures and study interventions/products. This will include aspects of the trial that are experimental, the probability for random assignment to treatment groups, any expected benefits, all possible risks (including a statement that the particular treatment or procedure may involve risks to the subject), the expected duration of the subject's participation in the trial, alternative procedures that may be available and the important potential benefits and risks of these available alternative procedures. available and, if the results of the trial are published, the subject's identity will remain confidential. Subjects will be informed whether private information collected from this research and/or specimens will be used for additional research, even if identifiers are removed.

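### The primary endpoint has two stool-collection rules (two or three at week 4), and the sections on entry disagree on whether a positive stool is needed before randomisation

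*Combined protocol and SAP*

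**What the plan says.** **Number of stools.**

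- Week 4, section 4.2.1 (Study Visit 2): "Two stools will be collected on consecutive days to quantify egg counts by Kato Katz". The screening paragraph of the same section also sets two, names week 4 among the time points, and has each stool smeared in duplicate.
- Week 4, section 7.4: "Three stools will be collected to quantify egg counts by Kato Katz". No site is singled out.
- Baseline, section 4.2.1: "Two stool samples (taken on consecutive days) will also be collected from every child who is CCA positive".
- Baseline, section 7.2: "Parents will be given two cups (three in the Philippines) to provide stool samples collected on different days".
- Section 3.2.1 defines cure as no eggs on Kato-Katz at four weeks and egg reduction as the percentage fall from baseline. It states no number of stools or slides and sets no condition on the baseline count.

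**Who may be randomised.**

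- Section 5.1 requires "infection of any intensity as determined by Kato-Katz".
- Section 14.3 agrees: "only those who have schistosomiasis based on stool examination are eligible to participate in the main study".
- Section 7.2 says: "Children with a positive antigen test will be considered positive for schistosomiasis and eligible for potential enrolment". There the stools serve only to measure intensity.
- Section 7.3 lists, for the enrolment visit at which the drug is given, stool "collection for parasitology by Kato-Katz if two stools not provided prior to enrollment". It mentions no wait for a slide result.

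Section 11.4 analyses all children as randomised, with complete cases at week 4.

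**The concern.** A child is cured if no slide shows an egg, so reading more stools finds more residual infection and lowers the observed cure rate. With two rules in force, the primary endpoint is not a single measurement. The absolute rate matters here because section 2.2 judges doses against an 85% cure benchmark. The egg reduction rate also compares two time points, which as written can rest on different numbers of stools.

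The entry conflict raises a second problem. A child with no eggs before treatment cannot show parasitological cure, yet the definition scores that child as cured on either dose if week 4 is also negative. Such children pull the dose difference towards zero. Their egg reduction rate has a zero denominator, and the plan has no rule for that.

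**Working it through.** **1. Rules side by side**

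| Time | Section 4.2.1 | Sections 7.2 and 7.4 |
|---|---|---|
| Baseline | 2 | 2 in Uganda, 3 in the Philippines |
| Week 4 | 2 | 3 |

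Under section 4.2.1 every child has 2 before and 2 after. Under section 7 a Ugandan child has 2 and 3, and a Philippine child 3 and 3. Nothing in the protocol says which section governs.

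**2. The plan's own sample size**

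Section 11.2 gives 173 per arm (80% power) and 232 per arm (90%) for 70% versus 82%, two-sided 5%. The pooled two-proportion formula gives 198 and 265, so the stated figures do not reproduce. One-sided 5% with continuity correction gives 172 and 232. That is a separate matter. Below I use the planned enrolment less the plan's 7% loss: 300 × 0.93 = 279 per dose.

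Power = Φ{[d√n − 1.96√(2p̄(1−p̄))] / √(p₁(1−p₁) + p₂(1−p₂))}

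With 0.70, 0.82, p̄ = 0.76 and n = 279: (2.004 − 1.184)/0.598 = 1.37, so power is 91.5%.

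**3. Two stools against three**

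Assumptions: stools are independent; each detects a residual infection with probability s, from 0.5 to 0.9 (the documents give no value); 70% and 82% were observed with two stools (section 11.2 does not say how many).

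Detection over k stools: S_k = 1 − (1 − s)^k. The observed uncured share with three stools is the two-stool share × S₃/S₂.

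| s | S₂ | S₃ | S₃/S₂ | Cure with three stools | Difference |
|---|---|---|---|---|---|
| 0.5 | 0.750 | 0.875 | 1.167 | 65.0% / 79.0% | 14.0 points |
| 0.7 | 0.910 | 0.973 | 1.069 | 67.9% / 80.8% | 12.8 points |
| 0.9 | 0.990 | 0.999 | 1.009 | 69.7% / 81.8% | 12.1 points |

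For s = 0.5, uncured 30% becomes 35.0% and 18% becomes 21.0%. The choice moves the absolute cure rate by 0.2 to 5 points.

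If 70% and 82% were instead observed with three stools, two would show 74.3% / 84.6% (s = 0.5) to 70.3% / 82.2% (s = 0.9). The difference is then 10.3 to 11.9 points, and power at 279 per dose is 85.4% to 91.2%.

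**4. Egg-negative children at baseline**

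Assumptions: a share f of those randomised has no eggs at baseline; all are scored cured; 70% and 82% hold in the rest. The documents give no value for f.

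Observed rates: f + (1 − f) × 0.70 and f + (1 − f) × 0.82. The difference is 0.12 × (1 − f).

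For f = 10%: 73.0% and 83.8%, difference 10.8 points, p̄ = 0.784. Power: (1.804 − 1.141)/0.577 = 1.15, or 87.5%. Leaving these children out of the analysis (279 × 0.9 ≈ 251 per dose, difference 12.0 points) gives 88.5%.

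**The case against.** The case for the plan has real force on several points.

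- A reader might infer that egg-negative children are eligible. Sections 5.1 and 14.3 exclude them. Section 7.2 speaks only of potential enrolment, as the first of two screening phases, and section 7.3 has the remaining criteria checked before enrolment. Taking stool at the visit also fits a child who already has one positive stool and is completing the intensity measure. What remains is conflicting wording: the phase-two checks listed in section 7.3 do not include a Kato-Katz result.
- A reader might infer that week-4 effort differs between sites and distorts the site interaction. The documents do not say so. Neither statement on week 4 separates the sites; site-specific counts appear at screening and at 12 months (section 7.6). Site and species are fully confounded by design in any case.
- A reader might discount 70% and 82% for missed infections and conclude that the trial loses power. Section 11.2 reports them as rates found in Uganda, so imperfect detection is already in them and the discount would be applied twice.
- The stool rule is the same for both randomised doses, so it does not bias the comparison towards either. For egg reduction, counts are averaged, so unequal numbers of stools mainly affect precision.
- The dilution figure depends on an assumed share, and on every such child staying negative at week 4. A lightly infected child may shed eggs then.

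All of this stands. It limits the size of the problem but resolves neither contradiction.

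**Conclusion.** The point holds as two inconsistencies that bear on the primary endpoint.

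First, week-4 stools are two in one section and three in another, and the definition of cure does not settle it. Depending on per-stool detection (0.5 to 0.9, assumed), the choice shifts the absolute cure rate by 0.2 to 5 points and changes the size of the dose difference, without favouring a dose.

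Second, sections 7.2 and 7.3 leave open a route to randomisation that sections 5.1 and 14.3 close. The documents do not show that any egg-negative child would enter, or how many. If some did, the cure denominator would be wrong and their egg reduction rate undefined. The loss at an assumed 10% share, 12.0 to 10.8 points and 91.5% to 87.5% power, is an illustration and not a forecast. Restricting the analysis recovers only part of that power, so its main gain is a valid denominator.

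**What to change.** 1. In sections 3.2.1, 4.2, 7.2 and 7.4, state one number of stools, with duplicate slides each, for primary cure and egg reduction. Make it the same at baseline and week 4 and at both sites. Use any additional stool only in a sensitivity analysis.
2. Align sections 7.2 and 7.3 with 5.1, so that a positive pre-treatment Kato-Katz is on record before a study number is assigned.
3. In sections 3.2.1 and 11.4, define the cure and egg reduction analyses as randomised children with eggs at baseline. This is a pre-treatment criterion, so the randomised comparison is preserved.

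The cost is mostly wording. Some children wait for a slide result, and an extra stool at one site may go unused in the primary analysis. If the common number is two, some detection is given up (step 3 of the working shows how much). The number should be fixed before collection, because week-4 stools that were not taken cannot be recovered later.
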